8.5. Study size

The study will involve approximately 300 patients recruited from approximately 30 participating sites.

This study will compare Xyntha vs. Eloctate /Adynovate among hemophilia A patients and Alprolix vs. BeneFIX among hemophilia B patients. For a mean difference comparing two independent means with the anticipated sample sizes (75 vs. 75; 150 total) with $\alpha=0.05$, two-sided, 80% power, the expected minimal detectable effect (MDE) would be Cohen's $d=0.46$. This study with the anticipated sample size is powered to detect at least a moderate effect size.

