### ***6.1.2. Bivariate Analyses***

Bivariate (BV) comparisons and descriptives can help provide initial insight into the dosing, health-related quality of life, resource utilization, and cost patterns associated with different hemophilia treatments (standard half-life vs. extended half-life). Bivariate comparisons, using chi-square tests or one-way ANOVA for categorical and continuous variables, respectively, will be conducted for each hemophilia subgroup (A and B).

The BV results will be used to feed into a more robust multivariable (MV) analysis to create a model to estimate health-related quality of life, resource utilization and costs, while controlling for covariates, associated with different hemophilia treatments.

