### ***6.2.2. Bivariate Analyses***

Differences among hemophilia patients on standard half-life vs. extended half-life treatments (hemophilia A: Xyntha vs. Adynovate or Eloctate; hemophilia B: Benefix vs. Alprolix) will be made with respect to demographics variables to assess for potential covariates to include

Protocol # B1821056  
 Statistical Analysis Plan

in subsequent modeling (*Table 2*). Chi-square tests and one-way ANOVAs will be used for categorical and continuous outcomes, respectively. Additionally, differences among treatment groups will also be made with respect to hemophilia specific characteristics (eg, disease severity, symptoms), attitudes towards infusions and physician relationship and outcomes (eg, number of infusions, health-related quality of life, healthcare resource utilization, total healthcare costs, total Rx costs, hemophilia healthcare costs, hemophilia Rx costs) to assess unadjusted differences using one-way ANOVAs (*Table 3-Table 7*).

These analyses will be conducted separately for hemophilia A and hemophilia B patients.

Note that healthcare costs and Rx costs will be obtained from claims data and may be limited by sample size as not every patient may be willing to provide that data. If sample sizes are very low, bivariate and multivariable comparisons may not be conducted; descriptive statistics will be provided instead.

**Table 2. Example bivariate Table: Patient demographics among hemophilia A patients by standard half-life vs. extended half-life treatment. Note: a similar table would be created for hemophilia B patients.**

	Treatment Group							
	Standard Half-Life		Extended Half-Life		Total			
	% / Mean	N/ SD	% / Mean	N/ SD	% / Mean	N/ SD		
Age								
Gender	Male							
	Female							
Marital Status	Married/partnered							
	Single/divorced/widowed							
	Declined to answer							
Race/Ethnicity	Non-Hispanic White							
	Non-Hispanic Black							
	Hispanic							
	Other ethnicity							
Education	4 years							
	Less than 4 years							
Household income	<25K							
	\$25K to <50K							
	\$50K to <75K							
	\$75K or more							
	Declined to answer							
Employment Status	Employed							
	Not Employed							

Protocol # B1821056  
 Statistical Analysis Plan

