**Table 3. Example bivariate table: Patient health characteristics, disease characteristics, and treatment history among hemophilia A patients by standard half-life vs. extended half-life treatment (from patient chart). Note: a similar table would be created for hemophilia B patients.**

	Treatment Group						p-value	
	Standard Half-Life		Extended Half-Life		Total			
	% / Mean	N/ SD	% / Mean	N/ SD	% / Mean	N/ SD		
Kogenate FS								
Kovaltry								
Monoclate-P								
Novoeight								
Nuwiq								
Recombinate								
Other, specify								
Was not taking another treatment previously								
Duration of former factor prescribed								
Reasons for discontinuation	Cost/insurance coverage issues							
	[IF PATIENT IS UNDER 18] Patient developed inhibitors to treatment							
	Doctor recommendation							
	Patient preferred a different infusion frequency							
	Other							
	Don't know							
Frequency of visits (non-infusion)	Several times a month							
	Once a month							
	Every three months							
	Every six months							
	Once a year							
	Less than once a year							

Protocol # B1821056  
 Statistical Analysis Plan

**Table 4. Example bivariate table. Patient health characteristics, disease characteristics, and treatment history among hemophilia A patients by standard half-life vs. extended half-life treatment (patient-reported). Note: a similar table would be created for hemophilia B patients.**

		Treatment Group							
		Standard Half-Life		Extended Half-Life		Total			
		% / Mean	N/ SD	% / Mean	N/ SD	% / Mean	N/ SD		
Severity	Mild hemophilia Moderate hemophilia Moderately severe hemophilia Severe hemophilia								
Clotting factor level	6% to 40% 1% to 5% Less than 1%								
Current treatment	Advate Adynovate Afstyla Eloctate Helixate FS Hemofil M Kogenate FS Kovaltry Monoclate-P Novoeight Nuwiq Recombinate Xyntha solofuse Other, specify								
Duration of current factor prescribed									
When infuse	On regular basis to prevent bleeding episodes Whenever or as needed when there is a bleeding episode Both, on a regular basis to prevent bleeding episodes as well as whenever as needed when there is a bleeding episode								
Prior treatment	Advate Adynovate								

Protocol # B1821056  
 Statistical Analysis Plan

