**Table 4. Example bivariate table. Patient health characteristics, disease characteristics, and treatment history among hemophilia A patients by standard half-life vs. extended half-life treatment (patient-reported). Note: a similar table would be created for hemophilia B patients.**

	Treatment Group							
	Standard Half-Life		Extended Half-Life		Total			
	% / Mean	N/ SD	% / Mean	N/ SD	% / Mean	N/ SD		
Afstyla								
Eloctate								
Helixate FS								
Hemofil M								
Kogenate FS								
Kovaltry								
Monoclate-P								
Novocight								
Nuwiq								
Recombinate								
Other, specify								
Was not taking another treatment previously								
Duration of former factor prescribed								
Clinical trials for receiving treatment	Yes							
	No							

**Table 5. Example bivariate table. Health-related quality of life among hemophilia A patients by standard half-life vs. extended half-life treatment (patient-reported). Note: a similar table would be created for hemophilia B patients.**

	Treatment Group							
	Standard Half-Life		Extended Half-Life		Total			
	Mean	SD	Mean	SD	Mean	SD		
for adults								
SF-36 Physical Component Summary Score								
SF-36 Mental Component Summary Score								
HAEM-A-QOL)								
caregiver reported for child								
SF-10 Physical summary score								
SF-10 Psychosocial health summary score								
HAEMO-QOL								

Protocol # B1821056  
 Statistical Analysis Plan

**Table 6. Example bivariate table. Patients' attitudes on factor use and physician relationship among hemophilia A patients by standard half-life vs. extended half-life treatment. Note: a similar table would be created for hemophilia B patients.**

		Treatment Group						p-value	
		Standard Half-Life		Extended Half-Life		Total			
		%	N	%	N	%	N		
Frequency of extra infusion used	Never								
	2 times								
	3 times								
	4 times or more								
Reasons for using extra infusion	Bleeding episode								
	Wanted additional protection before sport/activity								
	Felt pain (thought it was bleed)								
	Wanted extra protection for no specific reason								
Frequency of dose higher than prescribed	Never								
	1-2 times								
	3-4 times								
	5-6 times								
	7 or more times								
Reasons for higher dosing	Wanted additional protection before sport/activity								
	Felt pain (thought it was bleed)								
	Wanted extra protection for no specific reason								

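### SAP 6.2.2 assigns all of Tables 3-7 to one-way ANOVA, against the SAP's own rule: nominal rows cannot be analysed that way, and ordered items are given no ordinal test

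*SAP*

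**What the plan says.** SAP 6.1.2 gives the general rule for bivariate comparisons: "using chi-square tests or one-way ANOVA for categorical and continuous variables, respectively". SAP 6.2.2 repeats it directly after introducing Table 2: "Chi-square tests and one-way ANOVAs will be used for categorical and continuous outcomes, respectively". The next sentence then covers hemophilia-specific characteristics, attitudes to infusion, physician relationship and the outcomes. It compares the groups on all of these "to assess unadjusted differences using one-way ANOVAs", citing Tables 3 to 7, and names neither chi-square nor any ordinal method.

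Those tables are largely categorical. Some rows are nominal: factor product, symptoms, reasons for discontinuation, reasons for extra infusions, and the four physician-relationship statements. Others are ordered:

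- "Frequency of dose higher than prescribed" (Table 6) has five levels, from never to seven or more.
- "Frequency of visits (non-infusion)" (Table 3) has six levels, from several times a month to less than once a year.
- The extra-infusion frequency (Table 6) has four printed levels.

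Neither document names a rank test, a trend test or ordinal regression, or gives category scores. The adjusted models in SAP 6.2.3 and Table 8 do not list these three ordered items, so the bivariate test is the only comparison explicitly planned for them.

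**The concern.** Two rules within one section give different tests for the same rows. On a nominal row, one-way ANOVA compares means of arbitrary labels, and its p-value changes with the coding. On an ordered row the choice is between two imperfect tests. ANOVA treats the codes as equally spaced, although the visit levels are unevenly spaced in time and the dosing and extra-infusion items end in an open category. Chi-square ignores the order and spreads a directional question over three to five degrees of freedom.

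Extra infusions and higher-than-prescribed dosing bear on how the products are actually used, which is the subject of the primary objective. If the conflict stays, the test for these items could be chosen after the data are seen, between procedures whose power can differ by 20 points or more.

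**Working it through.** **The plan's own figure.** Protocol 8.5 uses "anticipated sample sizes (75 vs. 75; 150 total)" with two-sided alpha 0.05 and 80% power. MDE = (z0.975 + z0.80) × sqrt(2/75) = (1.960 + 0.842) × 0.1633 = 0.4575. The noncentral t gives 0.4605. Both round to the stated d = 0.46, so the figure reproduces. It applies to a difference in means, not to the ordered items.

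**Cost of ignoring order, analytic.** A 1-df test with 80% power has noncentrality λ = (1.960 + 0.842)² = 7.849. If the same λ is spread over k df, power = P(χ²(k, λ) > χ²(0.95, k)):

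| Levels | df | Chi-square power | Loss (points) |
|---|---|---|---|
| 2 | 1 | 80.0% | 0 |
| 4 | 3 | 64.5% | 15.5 |
| 5 | 4 | 59.5% | 20.5 |
| 6 | 5 | 55.5% | 24.5 |

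**Simulation.** 20,000 trials per setting, 75 vs 75. The documents give no category distributions, so those below are assumptions. The proportional-odds shift was tuned to about 80% Wilcoxon power (log odds ratio 0.81 to 0.86, that is, an odds ratio of about 2.25 to 2.36). ANOVA used codes 0, 1, 2 and so on.

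| Assumed reference distribution (%) | Chi-square | ANOVA | Wilcoxon | Chi-square loss vs Wilcoxon |
|---|---|---|---|---|
| 4 levels, equal | 63.8% | 79.8% | 79.9% | 16.1 |
| 4 levels, 60/20/12/8 | 64.5% | 78.8% | 80.5% | 16.0 |
| 5 levels, equal | 57.6% | 78.8% | 79.0% | 21.4 |
| 5 levels, 60/18/10/7/5 | 59.0% | 76.8% | 79.5% | 20.5 |
| 5 levels, 40/25/15/10/10 | 58.6% | 78.7% | 79.4% | 20.8 |
| 6 levels, equal | 54.2% | 79.2% | 79.6% | 25.4 |
| 6 levels, 3/7/30/40/15/5 | 54.2% | 78.6% | 80.5% | 26.3 |

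A latent normal shift of d = 0.46 gave Wilcoxon power of 69-76% and similar losses: 16.2-16.9 points on four levels, 21.3-22.1 on five and 25.7-27.2 on six. ANOVA stayed within 3 points of Wilcoxon throughout, with type I error 4.8-5.5%. In the uneven six-level case every simulated table had an expected count below 5.

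**Dependence on reference power.** On 4 df the analytic loss is 19 points when the 1-df test has 50% power, 22 at 70%, 16 at 90% and 11 at 95%.

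**Other patterns, five levels.**

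| Pattern | Chi-square | ANOVA | Wilcoxon |
|---|---|---|---|
| Only never vs any changes (60/16/10/8/6 vs 38/24.8/15.5/12.4/9.3) | 56% | 58% | 71% |
| Mostly the top category rises (50/20/15/10/5 vs 42/18/12/8/20) | 61% | 51% | 37% |
| Middle bulge (50/10/10/10/20 vs 30/25/20/15/10) | 88% | 7% | 18% |

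**Which row applies.** As read, Table 6 prints four levels for extra infusions (never, 2, 3, 4 or more), so the four-level loss applies. Protocol Appendix 2 collects five levels, including one time, separately for each of five reasons; on five levels the loss would be about 21 points. The missing row may have been lost when the PDF was read.

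**The case against.** The ANOVA sentence may be a drafting slip. The rule just before it and SAP 6.1.2 both send categorical variables to chi-square, and Table 6 has only percentage and count columns, which fit chi-square rather than means. This is a fair reading, but it does not settle the matter: the preceding sentence follows directly on Table 2 and can be read as confined to it, and the chi-square route still ignores order.

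A reader might infer that the plan as written gives up 20-27 points of power. The documents do not support that. The sentence names ANOVA, and two-group ANOVA on integer codes is close to a 1-df trend test, with valid size and almost full power for ordered shifts. The loss belongs to the chi-square route only, and it is smaller for the four printed levels.

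A reader might also infer that the study's dosing comparison is compromised. It is not. Infusions per month goes to an adjusted model (SAP 6.2.3, Table 8), as do claims-based visit counts. SAP 6.1.2 describes bivariate results as initial insight, and Table 6 is titled as attitudes. The stated motivation is dosing relative to labeling, which is not the same as use beyond the individual prescription.

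Finally, an ordinal test is not uniformly better. It loses to chi-square when mainly the top category rises, which would fit a subset of heavy users, and proportional odds adds an assumption. This stands.

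**Conclusion.** The point holds as a conflict in test assignment and a gap in method. ANOVA has no meaning for the nominal rows of Tables 3, 4 and 6. For the ordered items, ANOVA keeps its power against ordered shifts but relies on unstated equal-spacing scores. Chi-square would lose about 15-17 points on four levels, 20-22 on five and 25-27 on six. Those figures assume the category distributions shown, 75 patients per group, a consistent ordered shift and roughly 80% power for the ordinal test (69-81% across the simulated settings). They shrink at higher reference power and can reverse for non-monotone or top-category differences. The comparisons affected are secondary and unadjusted. The adjusted analysis of infusions per month and the stated d = 0.46 stand.

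**What to change.** In SAP 6.2.2, replace the blanket ANOVA sentence with a rule by variable type that agrees with 6.1.2:

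- Continuous variables: one-way ANOVA.
- Nominal items: chi-square, or an exact test when expected counts are small.
- Ordered items (extra infusions, higher-than-prescribed dosing, visit frequency): Wilcoxon rank-sum, or an unadjusted proportional-odds model reporting the common odds ratio with 95% CI. Name one of the two in advance.
- Don't-know responses: keep them out of the ordering. SAP section 5 makes them a separate category in bivariate analysis, which has no place on an ordered scale. Timing of diagnosis in Table 3 is an ordered item that prints such a row.
- Report full category percentages for every ordered item, so that a top-category or non-monotone difference stays visible.

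Reconcile the Table 6 levels with Protocol Appendix 2, and state how one extra-infusion frequency is derived from the reason-by-reason answers.

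The cost is SAP wording and a different procedure call, with no new data. The small downside is lower power than chi-square for non-monotone or top-category differences, plus the proportional-odds assumption if that model is chosen.

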8.3. Variables

Below is the current list of variables to be assessed in the in the study:

Physician Participants

Physician/Practice Characteristics

- Primary medical specialty;
- Board certification;
- Percentage of time spent in direct patient care;
- Percentage of their practice dedicated to the treatment of hemophilia;
- Number of moderate to severe hemophilia A and B patients currently managed;
- Number of hemophilia A and B patients currently participating in clinical trials;
- Insurance plans accepted.

Patient Treatment Pattern

- Current and previous hemophilia treatment;
- Reasons for discontinuation;
- Duration of treatment used;
- Whether prescription was prophylaxis or on-demand;
- Number of infusions per month prescribed;
- Frequency of doctor visits for management of hemophilia.

Patient Clinical Profile

- Height and Weight;
- Age of diagnosis;
- Primary symptoms;
- Disease severity;
- Joint health score;
- Comorbidities.

Patient Participants:

Patient Demographics

- Sex;
- Age;
- Race/ethnicity;
- Marital status;
- Household income;
- Education;*
- Employment status;*
- Health insurance type;
- Healthcare insurer;
- Pharmacy insurer.

*In the case of caregivers responding, caregiver's education and employment will also be collected.

Patient Clinical Profile

- Disease severity;
- Clotting factor level.

Patient Treatment

- When are infusions done;
- Number of infusions in a typical month;
- Previous and current hemophilia treatments;
- Duration of previous and current hemophilia treatments used;
- Recent Factor Use Behavior;
- Whether participated in clinical trials within the past 12 months.

Physician Patient Relationship

- Patient's relationship with his/her physician in regards treatment decisions for hemophilia rated as either paternalistic, informative, interpretive, or deliberate depending upon which relationship description the patient selects.

Validated Scales for Health-Related Quality of Life

- 36 Item Short Form Health Survey (SF-36 (adult)).³
- 10 Item Short Health Survey (SF-10 (caregiver reported for child)).⁴
- Hemophilia-Specific Quality of Life Index for Adults (HAEM-A-QOL (adult)).⁵
- Hemophilia-Specific Quality of Life Index (HAEMO-QOL (caregiver reported for child)).⁶

Health Insurance Claims Data from Patients

- Total services and healthcare costs (healthcare visits, factor).
- Hemophilia-specific services and costs (healthcare visits, factor).

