##### *Patient Treatment Pattern (from patient chart)*

- Current and previous hemophilia treatment
- Reasons for discontinuation
- Duration of treatment used
- Whether prescription was prophylaxis or on-demand
- Number of infusions per month prescribed

Protocol # B1821056  
Statistical Analysis Plan

- Frequency of doctor visits for management of hemophilia

*Patient Demographics (from patient chart)*

- Age
- Sex
- Race
- Weight
- Height
- Health insurance type

*Patient Clinical Profile (from patient chart)*

- Age of diagnosis
- Primary symptoms
- Disease severity
- Joint health score
- Comorbidities

Patient Participants (self-reported or caregiver reported):

*Patient Demographics*

- Sex
- Age
- Race/ethnicity
- Marital status
- Household income
- Education\*
- Employment status\*
- Health insurance type

Protocol # B1821056  
Statistical Analysis Plan

- Healthcare insurer
- Pharmacy insurer

\*In the case of caregivers responding, caregiver's education and employment will also be collected.

*Patient Clinical Profile*

- Disease severity
- Clotting factor level

*Patient Treatment*

- When are infusions done
- Number of infusions in a typical month
- Previous and current hemophilia treatments
- Duration of previous and current hemophilia treatments used
- Recent factor use behavior
- Whether participated in clinical trials within the past 12 months

*Physician Patient Relationship*

- Patient's relationship with his/her physician in regards treatment decisions for hemophilia rated as either paternalistic, informative, interpretive, or deliberate depending upon which relationship description the patient selects.

*Validated Scales for Health-Related Quality of Life*

*Global health-related quality of life scales*

36 Item Short Form Health Survey (SF-36; adult): The SF-36v2 is a multipurpose, generic health status instrument comprised of 36 questions. These items map onto eight health domains: physical functioning, physical role limitations, bodily pain, general health, vitality, social functioning, emotional role limitations, and mental health. In addition to these eight health domains, there are two component summary scores: the physical component summary (PCS) and the mental component summary (MCS).

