**6. STATISTICAL METHODOLOGY AND STATISTICAL ANALYSES**

**6.1. Statistical methods**

**6.1.1. *Descriptive Analyses***

Descriptive statistics (means and standard deviations for continuous variables and frequencies and percentages for categorical variables) will be reported for all study measures on the total sample and subgroups. This analysis of the distributions will be a part of testing of model assumptions and will help inform the appropriate modeling techniques.

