**Table 2. Example bivariate Table: Patient demographics among hemophilia A patients by standard half-life vs. extended half-life treatment. Note: a similar table would be created for hemophilia B patients.**

		Treatment Group							
		Standard Half-Life		Extended Half-Life		Total			
		% / Mean	N/ SD	% / Mean	N/ SD	% / Mean	N/ SD		
	Student								
Geographic Region	South								
	Northeast								
	Midwest								
	West								
Insurance	Coverage through employer								
	Coverage through spouse's/partner's employer								
	Coverage through parent's or legal guardian's employer								
	Individual/Family Plan- State Health Exchange								
	Individual/Family Plan- Self-purchased								
	Medicaid (MediCal for California)								
	Medicare								
	Veterans Administration (VA)/CHAMPUS								
	TRICARE								
	Not sure								
Healthcare insurer	Aetna								
	Anthem (Blue Cross and Blue Shield, Empire Blue Cross, Amerigroup, UniCare, CareMore, Wellpoint)								
	Centene								
	Cigna								
	Health Net								
	Human								
	Kaiser Permanente								
	Magellan Health								

Protocol # B1821056  
 Statistical Analysis Plan

**Table 2. Example bivariate Table: Patient demographics among hemophilia A patients by standard half-life vs. extended half-life treatment. Note: a similar table would be created for hemophilia B patients.**

	Treatment Group							
	Standard Half-Life		Extended Half-Life		Total			
	% / Mean	N/ SD	% / Mean	N/ SD	% / Mean	N/ SD		
Molina Healthcare								
UnitedHealth Group								
WellCare Health Plans								
Other, specify								
Different insurer covering prescription or pharmacy benefits?	Yes, different insurer for prescriptions							
	No, same insurer as medical							
	Don't know							
On patient assistance program for hemophilia medication?	Yes							
	No							
	Don't know							

**Table 3. Example bivariate table: Patient health characteristics, disease characteristics, and treatment history among hemophilia A patients by standard half-life vs. extended half-life treatment (from patient chart). Note: a similar table would be created for hemophilia B patients.**

	Treatment Group							
	Standard Half-Life		Extended Half-Life		Total			
	% / Mean	N/ SD	% / Mean	N/ SD	% / Mean	N/ SD		
BMI category	BMI: underweight							
	BMI: normal weight							
	BMI: overweight							
	BMI: obese							
	Declined to answer							

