### 6.2.3. Multivariable Analyses

For hemophilia A and hemophilia B cohorts separately, multivariable regression models will be conducted with treatment group (standard half-life vs. extended half-life) as the predictor of each outcome (ie, number of infusions, health-related quality of life, healthcare resource utilization, total healthcare costs, total Rx costs, hemophilia healthcare costs, hemophilia Rx costs) adjusting for the demographic and health history variables that have been identified as relevant covariates in bivariate analyses.

Generalized linear models will be used specifying the appropriate distribution (ie, negative binomial for skewed variables such as healthcare resource use and cost variables; identity link function for normally distributed variables such as health-related quality life). A regression summary results table with adjusted means, 95% CIs, standard errors, and p-values will be produced ([Table 8](#)).

**Table 8. Example regression summary table. Outcomes among hemophilia A patients by standard half-life vs. extended half-life treatment (adjusted for covariates). Note: a similar table would be created for hemophilia B patients.**

Outcome	Standard Half-Life				Extended Half-Life				p-value
	Mean	SE	Lower 95% CI	Upper 95% CI	Mean	SE	Lower 95% CI	Upper 95% CI	
Number of infusions per month									
SF-36 MCS/ SF-10 psychosocial									
SF-36 PCS / SF-10 physical									
HEAM-A-QOL / HAEMO-QOL									
Total Healthcare visits									
Total Healthcare costs									
Total Rx costs									
Hemophilia healthcare visits									
Hemophilia healthcare costs									
Hemophilia Rx costs									

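### Continuous body weight is collected but not pre-specified as a covariate in the cost models, which pool children and adults

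*SAP*

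**What the plan says.** Protocol 8.3 lists "Height and Weight" in the chart-based clinical profile. SAP 4.1 lists weight and height as separate items under the heading "Patient Demographics (from patient chart").

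SAP 6.2.2 compares the treatment groups on "demographics variables to assess for potential covariates to include" in later modelling and illustrates this with Table 2, where age is the first row and weight does not appear. Body size appears only in Table 3, as a BMI category with levels such as "BMI: normal weight". No cut-offs are given, for adults or for children. Table 3 is captioned "Example bivariate table: Patient health characteristics, disease characteristics, and treatment history among hemophilia A patients", so it is an example.

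SAP 6.2.3 fits one model per outcome within hemophilia A and within hemophilia B, "adjusting for the demographic and health history variables that have been identified as relevant covariates in bivariate analyses". The outcomes include total healthcare costs, total Rx costs, hemophilia healthcare costs and "hemophilia Rx costs". There is no adult/child stratum in SAP 3.2, in SAP 6.2.3 or in the cost rows of Table 8. Eligibility sets no age limit, caregivers answer for patients under 18, and SAP 4.1 describes child instruments that start at age 4.

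**The concern.** Resource utilization is part of the primary objective, and the SAP introduction says that factor products account for 45% to 93% of total medical costs. If the amount of factor used rises with body weight, a cohort with more children will look cheaper whatever product it uses. The cohorts are not randomised, so the child/adult mix may differ between standard and extended half-life patients. The plan does not commit to a body-size adjustment that would separate this from a product effect.

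BMI category is a weak stand-in because it is standardised for height: a young child and a much heavier adult can both be classed as normal. With adult cut-offs, many children would instead be classed as underweight. The SAP does not say which approach applies.

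The covariate rule adds to the problem. Choosing covariates by whether the treatment groups differ can miss a moderate imbalance. It also drops a variable that is balanced but strongly predicts cost, which loses precision. Adding weight after the cost results are seen would be open to challenge, whichever way it moved the answer.

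**Working it through.** **The plan's own figure.** Protocol 8.5 and SAP 2.2 give a minimum detectable effect of d = 0.46 for 75 vs 75, two-sided alpha 0.05, 80% power. Normal approximation: (1.960 + 0.842) × √(2/75) = 2.802 × 0.1633 = 0.457. The exact two-sample t calculation gives 0.4605. The stated figure is reproduced, and the factor 0.457 is reused below.

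**Assumptions.** The documents give no weight distribution, no share of children and no relation between weight and cost. I assume that factor cost is proportional to weight, mean weights of 30 kg (children) and 80 kg (adults), a log-weight SD of 0.3 to 0.5, and a residual log-cost SD (after weight) of 0.6 to 0.8.

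**Possible bias with no true product difference.** Mean weight in a cohort = p × 30 + (1 − p) × 80, where p is the share of children.

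- 30% vs 45%: 0.30 × 30 + 0.70 × 80 = 65.0 kg; 0.45 × 30 + 0.55 × 80 = 57.5 kg. Ratio 65.0/57.5 = 1.13.
- 40% vs 50%: 60.0 kg and 55.0 kg. Ratio 1.09.
- Equal shares: ratio 1.00.

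The direction depends on which cohort has more children. Varying the child mean over 25-45 kg and the adult mean over 75-85 kg, and dividing the cohort with more children by the other, gives 0.91-0.96 for shares of 25% vs 35%, and 0.84-0.91 for 20% vs 40%.

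**Precision.** Share of log-cost variance due to weight = w²/(w² + r²), with w the log-weight SD and r the residual SD. Detectable cost ratio = exp(0.457 × SD), with SD = √(w² + r²) unadjusted and SD = r adjusted.

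| w | r | Variance share | Unadjusted | Adjusted |
|---|---|---|---|---|
| 0.3 | 0.6 | 0.09/0.45 = 20% | 1.36 | 1.32 |
| 0.3 | 0.8 | 0.09/0.73 = 12% | 1.48 | 1.44 |
| 0.5 | 0.6 | 0.25/0.61 = 41% | 1.43 | 1.32 |
| 0.5 | 0.8 | 0.25/0.89 = 28% | 1.54 | 1.44 |

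The gain is small at w = 0.3. These figures use all 75 per cohort; SAP 6.2.2 warns that not every patient may supply claims.

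**Would the screen pick up the imbalance?** The SAP gives no threshold, so I assume p < 0.05. The SD of weight within a cohort is √(s² + p(1 − p) × 50²), where s is the SD within children and within adults, assumed to be 10-15 kg.

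- 30% vs 45%: the average variance is 672 to 797, so the SD is 25.9 to 28.2 kg. The 7.5 kg difference is 0.29 to 0.27 SD, and a t-test at 75 vs 75 flags it about 42% to 37% of the time.
- 40% vs 50%: SD 26.7 to 28.9 kg. The 5 kg difference is 0.19 to 0.17 SD, flagged about 21% to 18% of the time.

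So even with weight in the screening table, imbalances worth 9% to 13% of cost would more often be missed than caught.

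**How much the existing candidates recover.** A simulation with assumed height, BMI and age distributions and 20-50% children gave these shares of weight variance explained:

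| Predictors | Age-specific cut-offs for children | Adult cut-offs for all |
|---|---|---|
| BMI category alone | 48-55% | 78-80% |
| BMI category plus linear age | 68-73% | 82-85% |

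The two are a useful but incomplete proxy, and the result depends on a cut-off rule that the SAP does not state.

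**The case against.** A reader might infer that weight cannot be adjusted for, or enters the analysis only as a BMI category. The documents do not support that. SAP 4.1 classes weight as a chart demographic, SAP 6.1.1 promises descriptive statistics that "will be reported for all study measures on the total sample and subgroups", the tables are labelled as examples, and the covariate rule in 6.2.3 excludes no demographic variable. An analyst could add weight without departing from the SAP. This objection stands in full, and the point is confined to what is not pre-specified.

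A reader might also take it as given that weight is a main driver of factor use. The documents never say so. They link units only to infusion frequency, and the variable lists contain no prescribed dose in units. The relation is an assumption here, and the figures follow from it.

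Third, the bias scenarios are differences in age mix, and age is already in Table 2. If age enters the models, much of the bias and some of the precision gain is already dealt with. That is fair, but age faces the same uncertain screen. It is also true that this is a weakness of data-driven selection in general. Weight is one case where the remedy is simple and the data are already planned.

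Finally, the point does not touch the dosing outcome, which is modelled as infusions per month.

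**Conclusion.** The point holds as a gap in pre-specification. Nothing in the SAP guarantees that continuous weight, or age, is in the cost models, although children and adults are pooled and the example tables carry body size only as a BMI category without child cut-offs.

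If cost is proportional to weight and the assumed means of 30 and 80 kg apply, the spurious cost ratio is 1.13 for child shares of 30% vs 45% and 1.09 for 40% vs 50%. It is nil when the shares are equal. Under the assumed SDs, weight accounts for 12-41% of log-cost variance, and adjustment lowers the detectable ratio from 1.36-1.54 to 1.32-1.44. Both effects are smaller if age is already adjusted for. The documents give no figures to show which scenario applies, so these are illustrations of scale and not estimates of actual bias.

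**What to change.** - In SAP Table 3, add a row for weight in kg as a continuous variable. Keep the BMI category for adults only, or state the age-specific cut-offs used for children.
- In SAP 6.2.3, include log(weight) and age as fixed covariates in the Rx and hemophilia cost models, whatever the bivariate comparison shows.
- Optionally, add hemophilia Rx cost per kg as a supportive row.

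This is a change of SAP wording. Weight is already to be collected from the chart, so no new data are needed. The price is one or two degrees of freedom per model.
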